The study is a prospective cohort study comprised of participants between ages 25-75 presenting to Atlanticare Regional Medical Center interventional pain department and Philadelphia College of Osteopathic Medicine OMM Clinic between April 2021 and May 2021 with trigger point in the upper trapezius muscle. It is expected that approximately 60 patients will be enrolled to produce approximately 50 evaluable subjects.

Inclusion Criteria: The subjects will only be recruited into the study if they have met all the following criteria:

- Ages between 25 and 60 years.
- Previous or current diagnosis of MTrP in the upper trapezius region according to the criteria set by Simons et al.³
- 1 active/latent MTrP in the upper trapezius region

The diagnostic criteria to establish myofascial trigger point is adopted from Travell and Simons³ and include:

1. Presence of palpable taut band in the skeletal muscle
2. Presence of hypersensitive tender spot in the taut band
3. Presence of local twitch response upon stimulation of the taut band
4. Reproduction of referred pain upon palpation
5. Presence of spontaneous referred pain pattern

Exclusion criteria: Any subject that exhibits any of the following criteria will be excluded from the study:

- Pregnancy or immunocompromise
- Fever/infection
- Previous history of whiplash injury
- Previous history of cervical surgery, cervical radiculopathy, or myelopathy
- Severe disc or cervical lesion
- Evidence of cognitive deficit
- Degenerative or inflammatory disease of the cervical spine or shoulder, fibromyalgia, or neuromuscular diseases
- Use of medications (anticoagulants, anti-inflammatory etc.) or illicit drug use (1 week prior to treatment or follow up)
- Received treatment for MPS a month before the study recruitment

All the patients of interest that present to AtlantiCare Regional Medical Center pain clinic and Philadelphia College of Osteopathic Medicine OMM Clinic that meet the relevant inclusion and exclusion criteria will be invited to participate in this study. The subjects will be informed of the purpose of the study and asked for informed consent. If recruited into the study, they will be administered a pre-intervention survey. Subjects will then be managed according to standard of care by their point of care physician. Following the intervention they will be administered a post-intervention survey immediately following the intervention and one-week post.

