OMT Trigger Point Statistical Analysis Plan Cover Page

Trial Name: Treating Trigger Points: Comparing Muscle Energy Techniques vs. Lidocaine Needling Technique for Pain Control and Quality of Life Measures.

NCT #: NCT05009264

Document Date: August 23, 2022

A comparative study of muscle energy technique and lidocaine injections on treating trigger points

Introduction

Myofascial pain syndrome is one of the most common musculoskeletal disorders seen in the aging US population ^{1,2}. It's characterized by myofascial trigger points (MTPs) which were first defined by Simons et al. (1999) as hyperirritable nodules in a taut band of skeletal muscle, associated with pain on manual stretching, contraction, or stimulation of the muscle³. Trigger points are further classified into active and latent based on their clinical features ⁴. Active MTPs are characterized by spontaneous pain at rest with referred pain on palpation whereas latent MTPs produce pain on palpation in addition to restriction of range of motion ^{2,4-7}. Studies have showed that the upper trapezius is one of the most common muscles affected by myofascial pain syndrome ^{8,9} leading to referred pain manifesting as headaches and stiff neck.

Currently, there are a variety of treatment options for MTPs including lidocaine injections, dry needling, osteopathic manipulative treatment, massage therapy, ultrasound therapy, and pharmacotherapy etc. There have been many studies investigating the safety and efficacy of dry needling and lidocaine trigger point injection techniques in the treatment of MTPs¹⁰⁻¹⁸. It has been demonstrated that both dry needling and lidocaine injections were equally effective in reducing symptoms associated with MTPs; the mechanical disruption of the taut fibers due to the effect of the needle and the depth of adequate penetration resulted in more pain reduction, rather than the substance actually delivered into the muscle ¹⁹⁻²⁴. Some authors also suggested the importance of a local twitch response (LTR); which is an observable contraction of the taut region of the muscle band upon stimulation during dry needling technique, indicating maximum effectiveness of the treatment ^{19,25}. However, a recent systemic review found that LTR during dry needling treatment was unnecessary and not required for management of myofascial pain syndrome ²⁶.

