On the other hand, there has been less research investigating the effects of manual treatment on trigger points. Travell and Simons initially treated trigger points with ischemic compression but later changed their recommendation to applying gentle digital pressure to trigger points ²⁷. A recent study exploring the traction-compression-stretch technique (TTCE) compared to ischemic compression showed some, albeit minor, increased outcome measures (pain pressure threshold) warranting clinical investigation ⁶. Another study compared active release and muscle energy techniques in treating latent trigger points of the upper trapezius and found that both techniques were equally effective in increasing cervical range of motion and decreasing pain and upper trapezius thickness⁷. Other studies have also shown interest in similar osteopathic manipulative techniques such as counterstrain, myofascial release, facilitated positional release and high velocity-low amplitude thrust techniques for treating trigger points^{3,27-29}.

There is no consensus as to which treatment method is superior, leaving the method of treatment up to the discretion of the individual physician, rather than the characteristics of the trigger point itself. Often, determination of treatment method is dependent upon the training received by a physician. There are currently no studies evaluating the efficacy of these various treatment options, specifically osteopathic manipulative treatment vs. trigger point injections. Thus, the intention of the present study was to compare the efficacy of muscle energy techniques vs. lidocaine for the treatment of MTPs in the upper trapezius region.

Study Objective

The primary aim of this study is to compare osteopathic manipulative treatment and lidocaine injection technique for treatment of myofascial trigger points in the upper trapezius region.

Study Design

The study is a prospective cohort study containing of participants between ages 25-65 age range that presented to Atlanticare Regional Medical Center pain management clinic and Philadelphia College of Osteopathic Medicine Osteopathic Clinic between November 2021 and February 2022 with trigger point in the upper trapezius muscle.

Inclusion Criteria: Subjects were recruited into the study if they met all of the following criteria:

- Age between 25 and 65 years.
- Previous or current diagnosis of MTP in the upper trapezius region according to the criteria set by Simons et al.³

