To investigate the treatment effect between groups across time, a mixed design two factor ANOVA was utilized. As expected, due to small sample size, heterogeneity of covariance matrices was detected. This is considered a limitation of the study. Also, since a repeated measures design was implemented across three time periods, Mauchly's test of sphericity was examined and found to be significant ($p = .042$). This indicates that sphericity cannot be assumed, so a Greenhouse-Geisser statistic was computed. A statistically significant interaction effect was detected, $F(1.65, 56) = 3.90, p = .034$. Due to p-value being less than 0.05, we can confidently reject the null hypothesis and accept the alternative hypothesis.

[figure not shown]
Table 1.

Sociodemographic Data	Mean (SD) or Number (%)		P value
	OMM (n = 21)	Lidocaine (n = 10)	
Sex (%), n = 31 (100%)	21 (100)	10 (100)	
Male, n = 7 (22.6%)	5 (23.8)	2 (20)	
Female, n = 24 (77.4%)	16 (76.2)	8 (80)	
Age, y			
Subjects from 20 – 29 y, n = 22 (71%)	21 (100)	1 (10)	
Subjects from 30 – 39 y, n = 1 (3.2%)	0	1 (10)	
Subjects > 60y, n = 8 (25.8%)	0	8 (80)	
Ethnicity			
Caucasian, n = 20 (64.5%)	11 (52.4)	9 (90)	
African American, n = 1 (3.2%)	1 (4.8)	0	
Latino or Hispanic, n = 4 (12.9%)	3 (14.3)	1 (10)	
Asian, n = 6 (19.4%)	6 (28.6)	0	
Pain Intensity			
Pre-intervention	2.76 (1.8)	7 (2.8)	
Post-intervention (immediate)	1.86 (0.9)	6.6 (2.3)	0.026
Post-intervention (one week)	1.81 (2.0)	4 (2.2)	0.062

Table 2.

	Group	Mean	Std. Deviation	N
Pre-intervention Pain	OMM	2.76	1.84	21
	Lidocaine	7.00	3.04	9
	Total	4.03	2.96	30
Post-intervention immediate pain	OMM	1.86	0.96	21
	Lidocaine	6.56	2.45	9
	Total	3.27	2.66	30
Post-intervention 1 week pain	OMM	1.81	2.01	21
	Lidocaine	4.00	2.17	9
	Total	2.47	2.27	30

Figure 1.

Discussion

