The goal of this study was to demonstrate the efficacy of OMT, compared to lidocaine with dry needling injection techniques, in the treatment of trapezius MTP. The results of the study showed that both lidocaine with dry needling and OMT were successful in reducing pain related to myofascial trigger points. However, neither of the two techniques demonstrated discrete superiority to one another. Although, this was not an intent of the study. The primary outcome of interest was pain intensity levels. There was a larger degree of pain reduction in the OMT group immediately post-intervention whereas lidocaine with dry needling showed larger reduction in one-week post-intervention pain levels. In the wake-throes of an opioid epidemic, the search for suitable, effective alternatives that provide non-opioid treatment for pain are an added benefit in patient centered care.

When Travell and Simons first described the concept of myofascial trigger points, they proposed an 'integrated hypothesis' which included local myofascial tissues, genetics, neuromechanical and biochemical factors as precipitating factors in the formation of trigger points^{30,31}. In Travell's ATP energy crisis model³², triggers points were described as focal areas of hypoxia and thus OMT aimed at increasing oxygenation such as gentle traction and pressure release received acceptance. Various studies^{30,32-35} have demonstrated the utility of OMT in treating trigger points. As demonstrated in the results, OMT yielded significant reductions in pain intensity immediately post intervention and one week post intervention. The results of this study are in concordance with other similar studies. Although we hypothesized that OMT would be more as effective as lidocaine for treatment of MTP, we demonstrated that these two treatment methods both provide appropriate relief of musculoskeletal pain. This reflects the validity of OMT in the outpatient clinic, which is a suitable alternative for treatment of MTP. Equal efficacy of OMT for MTP treatment gives patients and physicians the option to elect for a non-invasive, low cost treatment.

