We specifically note that this is a suitable treatment modality for all physicians, both osteopathic and allopathic, as we merge our skill sets over time in a unified manner. As mentioned, the training of a physician usually dictates the management decisions regarding MTP treatment. This study was conducted in a post graduate training institution that has multiple specialty programs with osteopathic recognition. In the single accreditation system, collaborating with allopathic physicians and exposing allopathic residents to osteopathic treatment options was viewed an advancement for patient centered care and osteopathic awareness. As more allopathic physicians expand their skill sets and complete OMT courses, demonstrating the efficacy of a common treatment modality compared to OMT will assist with treatment choice. Comparable efficacy of both options will help patients choose the option that best meets their needs and physicians choose the option that best augments their skill set.

Being a pilot study, we anticipated a considerable degree of limitations throughout the study. Limitations include but are not limited to low sample size, majority female participants, and substantial difference in mean age between the two groups. Additionally, the OMT intervention group had a significantly lower mean pre-intervention pain level compared to the lidocaine group which made it difficult to do a true comparative analysis between groups. However, as a pilot study, demonstration of OMT non-inferiority compared to a standard treatment modality, creates a stepping stone for future research to investigate the comparative efficacy of OMT on a larger scale and we therefore anticipate future trials with larger number of participants to demonstrate more significant data and results.

Conclusion

Based on our study, OMT has comparable value with lidocaine injection technique as a treatment modality for active TrPs in the upper trapezius region. Both techniques demonstrate considerable decrease in pain intensity from baseline and thus it allows for increased collaboration between osteopathic and allopathic practitioners to promote patient centered care.

References

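### The SAP's claims for OMM carry no age limit, but every OMM patient was in the 20–29 band, nobody was aged 40–60, and the groups share only one age band (21 versus 1 patients)

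*SAP*

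**What the plan says.** **Population.** The SAP's Study Design describes "participants between ages 25-65 age range", and its inclusion criterion is "Age between 25 and 65 years". The protocol gives two other ranges: "The study is a prospective cohort study comprised of participants between ages 25-75" in Study Design and "Ages between 25 and 60 years" under Inclusion Criteria.

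**Patients enrolled.** In SAP Table 1 the first age row begins "Subjects from 20 – 29 y, n = 22 (71". It holds all 21 OMM patients and 1 of the 10 lidocaine patients. The other rows hold 1 patient aged 30–39 and 8 over 60, all in the lidocaine group. Baseline pain was 2.76 (SD 1.84) in the OMM group and 7 in the lidocaine group.

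**Claims.** The Discussion says of the results: "This reflects the validity of OMT in the outpatient clinic, which is a suitable alternative for treatment of MTP". It goes on to assert equal efficacy and to offer this as a basis for patients and physicians to choose between the treatments. The Conclusion states that "OMT has comparable value with lidocaine injection technique as a treatment modality for active TrPs in the upper trapezius region".

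**Caveats.** The limitations paragraph names low sample size, a female majority, the difference in mean age, and the lower baseline pain in the OMM group, which it says hampered comparison. The Results state that the groups did not differ significantly on sociodemographic data.

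**The concern.** There are two separate questions: to whom the OMM result applies, and whether the two groups can be compared. The limitations paragraph addresses only the second. A reader told that mean ages differed substantially would not learn that no OMM patient was 30 or older, or that the middle of the eligible age range is empty in both groups.

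The Discussion frames its claims as help in choosing a treatment. Most lidocaine patients were over 60, so a clinician would naturally apply the alternative to patients of that age. The study has no OMM outcome for any of them. The sentence reporting no significant sociodemographic difference makes this harder to see, because it suggests that age was balanced.

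**Working it through.** **1. Reproduce Table 1.** The inputs are the age rows of Table 1 and the enrolment counts in the SAP's Results (21 OMM, 10 lidocaine).

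| Age band | OMM | Lidocaine | Total |
|---|---|---|---|
| 20–29 | 21 | 1 | 22 |
| 30–39 | 0 | 1 | 1 |
| over 60 | 0 | 8 | 8 |
| Sum | 21 | 10 | 31 |

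The percentages agree with the SAP: 22/31 = 71.0%, 1/31 = 3.2%, 8/31 = 25.8%; OMM 21/21 = 100%; lidocaine 10%, 10% and 80%.

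**2. Find the gaps.** Aged 40–60 in either group: 31 − (22 + 1 + 8) = 0. OMM patients aged 30 or older: 21 − 21 = 0.

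**3. Age coverage under each stated limit.** Counting whole years of age inclusively, and assuming that every OMM patient met the minimum age of 25, OMM covers ages 25–29 (5 years) and the empty span 40–60 is 21 years.

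| Stated range | Years of age | OMM coverage | Empty 40–60 |
|---|---|---|---|
| 25–65 (SAP) | 41 | 5/41 = 12% | 21/41 = 51% |
| 25–60 (protocol, inclusion) | 36 | 5/36 = 14% | 21/36 = 58% |
| 25–75 (protocol, Study Design) | 51 | 5/51 = 10% | 21/51 = 41% |

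These are shares of the eligible age span, not of patients. The finding is the same under all three ranges.

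**4. Overlap between groups.** The 20–29 band is the only one with patients from both groups: 21 OMM and 1 lidocaine. One lidocaine patient was lost before one week and that patient's age is not given, so at one week the band holds at most 1 lidocaine patient.

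**5. Test of age balance.** The SAP's Data Analysis names the Fisher test for sociodemographic data, with alpha 0.05. Table 1 as available to me shows no p-value for age, so there is no SAP figure to reproduce. With the margins fixed, the probability of the observed table is

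P = C(22,21) × C(1,0) × C(8,0) / C(31,21) = 22 / 44,352,165 = 4.96 × 10⁻⁷.

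No other table with these margins is as improbable, so this is also the exact p-value. As a check, the Pearson chi-square is 26.63 on 2 df, p = 1.6 × 10⁻⁶. The statement of no significant difference does hold for sex (5/21 versus 2/10 male, Fisher p = 1.0), but not for age.

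**The case against.** The SAP is more candid than a quick reading suggests. The Conclusion is tied to this study and confined to active trigger points in the upper trapezius. The broadest wording is in the Discussion. The low OMM baseline pain is disclosed, the list of limitations is expressly not exhaustive, and the study is called a pilot that needs larger trials. All of this stands, but none of it sets an age limit or reports that OMM was not observed at 30 or over.

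A reader might go further in several ways that the documents do not support:

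- **That OMM fails in older patients.** No data bear on whether response depends on age. The finding is an absence of observation.
- **That the trial missed its target population.** The Introduction calls the condition "one of the most common musculoskeletal disorders seen in the aging US population", but that is background. The eligibility criteria define the population.
- **That OMM patients had mostly mild pain, or that none had severe pain.** Only a mean and SD are given, with no individual scores or severity categories.
- **That ineligible patients were treated in the OMM group.** The 20–29 band starts below the minimum age of 25, but the table does not show that anyone was under 25.
- **That adding an age range to each sentence is enough.** For the comparative sentences this would leave a claim of comparable value in patients aged 20–29 resting on 21 versus 1 patients. Each treatment was also given at only one site, so narrowing by age would not separate treatment from clinic either.

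**Conclusion.** The concern holds as an overreach in reporting. The OMM within-group result comes from 21 patients, all under 30, with mean baseline pain 2.76 (SD 1.84). There is no OMM observation at 30 or over and no observation of either treatment at 40–60. The comparative claims lack support within the sample too, because age is almost fully confounded with treatment: 21 of 21 OMM patients but 1 of 10 lidocaine patients were in the 20–29 band. The statement of no significant sociodemographic difference is contradicted by Table 1 for age (Fisher p about 5 × 10⁻⁷).

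This rests on the Table 1 age bands being correct as printed. It does not depend on which of the three age ranges applied. No outcome estimate or outcome test changes. What changes is what may be concluded from them, together with the balance statement.

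**What to change.** 1. **Within-group OMM result.** In the Discussion and Conclusion, limit it to patients under 30 with mean baseline pain 2.76 (SD 1.84). Report the actual minimum and maximum age of the OMM group, since the 20–29 band starts below the minimum age. State that no OMM patient was 30 or older and that no patient in either group was aged 40–60.
2. **Comparative claims.** Remove the statements that OMT is a suitable alternative, has equal efficacy and has comparable value. Treat the Discussion's sentences on comparable efficacy and non-inferiority in the same way. Do not restrict them to ages 20–29. Give the reason: the only shared age band holds 21 OMM patients and 1 lidocaine patient.
3. **Sociodemographic statement.** Correct the Results sentence to say that the groups differed markedly in age, and give the exact p-value.
4. **Age limits.** Reconcile 25–60 and 25–75 in the protocol with 25–65 in the SAP, and state which limit was in force during recruitment. This bears on the lidocaine group: the 8 patients over 60 fall outside the protocol's inclusion criterion as written, but could fall within either of the other two ranges.

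The work is rewording, plus reading the recorded ages. No new data are needed. The cost to the sponsor is a narrower claim.

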Participants presenting to the Atlanticare Pain Management clinic received a lidocaine injection after dry needling into the location of the MTP by a board-certified pain management physician. First, the upper trapezius MTP was identified and isolated. After application of a coolant to numb the area, the isolated trigger point was penetrated using a 30-gauge needle, to a depth adjusted depending on the patient, into the subcutaneous tissue. The duration of treatment was approximately 1-2 minutes. Once the myofascial tension was relieved, 2 mL of 0.5% lidocaine was injected into the MTP.

After their respective interventions, the patient completed an immediate post-intervention survey, consisting of a 0-10 pain scale. Finally, approximately 7-10 days after the intervention, patients were contacted by telephone to complete the one-week post-intervention survey consisting of a 0-10 pain scale.

Outcome Measures

Pain intensity; measured using a point system; where 0 = no pain and 10 = maximum pain. Although this is a subjective measurement by the patient, we are interested in looking at the difference between pre- and post-intervention pain intensity ratings.

Data Analysis

The data was analyzed using R software. Values of interest include mean, median, standard deviation, normal distribution, confidence intervals etc. Intergroup and intra-group comparisons were conducted using independent t-tests and paired t-tests, respectively. Alpha level is set at 0.05 and p values less than that will be considered statistically significant. A descriptive analysis of the outcome variables was conducted to compare between the intervention groups. The homogeneity of sociodemographic data (age, sex, comorbid conditions) and outcome measures were analyzed using the Fischer test and Pearson chi square test, respectively.

The outcome measures were analyzed separately in both treatment groups. The contrast between the treatment groups was analyzed. A univariate analysis of the difference of the outcome variables at the different time points (before the intervention, immediately after the intervention, and a week post the intervention) were obtained through the student *t*-tests. A multivariate analysis was carried out using multiple logistic regression models with age, sex, and intervention group (Injection = 0, OMM = 1) factored as the independent variables.

Results

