The study was completed at two primary locations. There were a total of 10 eligible participants from the lidocaine treatment group and 21 eligible participants from the OMM treatment group enrolled after screening for the inclusion and exclusion criteria. 1 subject from the lidocaine treatment group was lost during follow-up at one week post intervention and thus excluded from the per protocol analysis of the study. The remaining participants' data were analyzed in SPSS 26. No significant difference was found between the two groups in regard to sociodemographic data (Table 1). At baseline, the OMM group had a mean pain intensity level of 2.76 (SD 1.8) while the lidocaine treatment group had a mean pain intensity level of 7 (SD 2.8). Descriptive statistics of pain intensity between the two groups demonstrate considerable variance (Table 2).

Within the OMM group, an independent samples t-test found a statistically significant difference between the pre-intervention and immediate post-intervention pain levels, $t(20) = 2.10, p = .048$. The mean pre-intervention pain level ($M = 2.76, SD = 1.84$) was significantly higher than the immediate post intervention pain level ($M = 1.86, SD = 0.96$). An independent samples t-test found a statistically significant difference between pre-intervention and one-week post-intervention pain levels, $t(20) = 2.68 p = .014$. The mean pre-intervention level of pain ($M = 2.76, SD = 1.84$) was significantly higher than one-week post-intervention ($M = 1.81, SD = 2.01$).

Within the lidocaine group, an independent samples t-test did not demonstrate a statistically significant difference between pre-intervention and immediate post-intervention pain levels, $t(20) = 1.17, p = 0.27$. The mean pain level pre-intervention ($M = 7, SD = 2.87$) was higher than immediately post-intervention ($M = 6.60, SD = 2.32$). When evaluating the difference in level of pain from pre-intervention to one-week post-intervention, an independent samples t-test was not statistically significant, $t(20) = 2.16 p = .062$. The mean level of pain pre-intervention ($M = 7, SD = 2.87$) was higher than one-week post-intervention ($M = 4, SD = 2.18$). Pain intensity between the two groups are also demonstrated graphically in Figure 1, with time point one corresponding to pre-intervention, two corresponding to immediately post-intervention and three corresponding to 1 week post intervention.

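### The SAP concludes that both treatments reduced pain, but its own lidocaine tests miss the 0.05 level and no untreated group exists, so the reported results do not support that conclusion

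*SAP*

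**What the plan says.** SAP, Data Analysis, sets the decision rule: "Alpha level is set at 0.05 and p values less than that will be considered statistically significant". It also names the tests: "Intergroup and intra-group comparisons were conducted using independent t-tests and paired t-tests, respectively". Within-group changes were therefore to be tested with paired t-tests.

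SAP, Results, reports for the lidocaine group that the immediate comparison "did not demonstrate a statistically significant difference between pre-intervention and immediate post-intervention pain levels" (t = 1.17, p = 0.27). For baseline to one week, "an independent samples t-test was not statistically significant" (t = 2.16, p = .062). Both lines print 20 degrees of freedom. Both OMM comparisons are reported as significant (p = .048 and p = .014).

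SAP, Discussion, then says the results showed that "both lidocaine with dry needling and OMT were successful in reducing pain related to myofascial trigger points". Later in the same section the two methods are said to have been shown to give suitable relief. The Conclusion adds: "Both techniques demonstrate considerable decrease in pain intensity from baseline".

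The only groups are two active treatments, each given at its own clinic (Protocol, Intervention; SAP, Study Design). Neither document describes an untreated or sham group.

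**The concern.** The Discussion and Conclusion use the language of proof for both groups. For lidocaine, the SAP's own tests at its own alpha do not supply that proof.

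The Discussion also words the falls as effects of treatment. A fall from baseline in people who attend a clinic with a painful trigger point can come from natural course, regression to the mean or placebo response as well as from treatment. Without an untreated or sham group these cannot be separated, in either arm.

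The limitations paragraph at the end of the Discussion covers small numbers, the sex mix, the age gap and the baseline pain gap. It mentions neither the two non-significant lidocaine tests nor the missing untreated group.

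The statement that both treatments work is one support for presenting OMM as an alternative of similar value, so a reader choosing between treatments would rely on it.

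**Working it through.** **Inputs (SAP, Results and Table 2).**
- Lidocaine means: 7.00 at baseline, 6.60 immediately (10 patients), 4.00 at one week (9 patients, after one loss). The baseline mean is 7.00 for both the 10 and the 9.
- OMM means: 2.76, 1.86 and 1.81 (21 patients).
- t values: lidocaine 1.17 and 2.16; OMM 2.10 and 2.68.

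**Step 1: reproduce the reported p-values.** Two-sided p = 2 × P(T > t).

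| Comparison | t | p at printed df 20 | p at paired df (n - 1) | Reported p |
|---|---|---|---|---|
| OMM immediate | 2.10 | 0.0486 | same (df 20) | .048 |
| OMM one week | 2.68 | 0.0144 | same (df 20) | .014 |
| Lidocaine immediate | 1.17 | 0.256 | 0.272 (df 9) | 0.27 |
| Lidocaine one week | 2.16 | 0.043 | 0.063 (df 8) | .062 |

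Allowing for rounding of t (2.155 to 2.165), df 8 gives 0.0623 to 0.0633, which agrees with .062. The printed df 20 does not agree for either lidocaine line. It is the correct paired df only for the 21 OMM patients.

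**Step 2: were the tests paired?** The Results call all four tests independent-samples tests. Running that test on the printed means and SDs gives:
- Lidocaine immediate: t = 0.34 (reported 1.17).
- Lidocaine one week: t = 2.41 to 2.54, p = 0.028 to 0.021, depending on whether 9 or 10 baseline values are used (reported t = 2.16).
- OMM: t = 1.99 and 1.60 (reported 2.10 and 2.68).

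None matches. The reported figures fit the paired tests named in Data Analysis.

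**Step 3: size and precision.** Standard error = mean change / t. 95% CI = mean change ± t(0.975, n - 1) × standard error.

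| Change from baseline | Fall | % of baseline | SE | Multiplier | 95% CI |
|---|---|---|---|---|---|
| Lidocaine immediate (n = 10) | 0.40 | 5.7 | 0.40/1.17 = 0.342 | 2.262 | -0.37 to 1.17 |
| Lidocaine one week (n = 9) | 3.00 | 43 | 3.00/2.16 = 1.389 | 2.306 | -0.20 to 6.20 |
| OMM immediate (n = 21) | 0.90 | 33 | 0.90/2.10 = 0.429 | 2.086 | 0.01 to 1.79 |
| OMM one week (n = 21) | 0.95 | 34 | 0.95/2.68 = 0.354 | 2.086 | 0.21 to 1.69 |

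Both lidocaine intervals include zero; both OMM intervals exclude it, the immediate one only just.

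**Step 4: does another reported test fill the gap?** The group-by-time interaction (p = .034) asks whether the two groups changed differently. It does not test whether the lidocaine group changed, and it compares two active arms, so it says nothing about treatment against no treatment.

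**The case against.** The strongest reply is that the Conclusion's sentence describes change from baseline and does not claim significance. The lidocaine mean fell by 3.00 points at one week, the largest change reported. As a description of that point estimate, calling the fall considerable is fair. This stands for one week. It does not stand for the immediate lidocaine change of 0.40 points, nor for the Discussion, which words both results as demonstrated treatment success.

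The SAP also reports the two lidocaine tests openly, uses the language of significance only for OMM, and calls the study a pilot. That is to its credit, but the summary statements do not carry those qualifications forward.

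Four stronger readings are tempting, and the documents support none of them.
- *The conclusion contradicts the results, or lidocaine was shown not to work.* A p-value of .062 in 9 patients, with an interval reaching 6.20 points, is imprecise. It is not evidence of no fall.
- *The missing untreated group contradicts a fall from baseline.* It blocks attribution to treatment, equally in both arms. The fall itself can still be reported.
- *The one-week lidocaine result was significant, because t = 2.16 on the printed 20 df gives p = 0.043.* Nine pairs cannot yield 20 df, and the reported p-value fits 8.
- *Correcting this settles whether the treatments are comparable.* That is a between-group question. A non-significant change within lidocaine shows neither that OMM is better nor that it is worse.

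Nor can the documents show how much of any fall is regression to the mean. They give no usual pain level and no retest correlation, and eligibility sets no minimum pain score.

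**Conclusion.** The point holds as a failure of support. At the SAP's own 0.05 level, no statistically significant reduction was shown for lidocaine at either time. The immediate change is small (0.40 points, about 6% of baseline), and the one-week change is large but very imprecise (3.00 points, interval just including zero). For OMM both falls are significant, at about 0.9 points each, but they too are uncontrolled. The claims that both treatments succeeded and both give relief therefore go beyond the reported results.

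This rests on two assumptions: that the tests were paired and two-sided, which the recomputed p-values bear out, and that the printed means and t values are correct. The immediate lidocaine interval uses the 10 patients behind the printed mean of 6.60. Using the 9 in Table 2 (fall 0.44, same t, df 8) gives -0.43 to 1.31 and the same conclusion.

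**What to change.** Make these changes in one edit of the SAP.

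1. In the Discussion and Conclusion, replace the sentences claiming success, relief and considerable decrease for both techniques with the four changes and their 95% CIs from the second table above, each with its n.
2. Add text such as: *No statistically significant reduction in pain was shown for lidocaine at either time; the one-week estimate is imprecise. All four figures are uncontrolled changes from baseline and are not attributed to treatment.*
3. Add the absence of an untreated or sham group to the limitations.
4. In Results, correct the lidocaine degrees of freedom from 20 to 9 (immediate) and 8 (one week), after checking the analysis output. Otherwise the new sentence would stand beside a printed t and df that imply p = 0.043.
5. In Results, describe all four within-group tests as paired, as Data Analysis specifies.

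No new data, patients or analyses are needed: four intervals, two df corrections and a few sentences. The real cost is a less favourable stated conclusion.
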